### 7.2 Duration of Follow-Up

Patients will be followed for adverse events for 30 days after their last dose of study medication. However, if a patient experiences an adverse event >30 days after their last dose of study medication that is felt to be, in the opinion of the investigator, possibly, probably or definitely related to study therapy, the adverse event should be reported.

**NOTE:** Pregnancy within 180 days for WOCBP and for 120 days for a female partner of child-bearing potential after the final study drug administration will be reported and followed per Section 8.6.

Patients should be followed every 3 months from end of treatment for 2 years, then every 4 months for 1 year, then every 6 months for 1 year, then annually for progression and survival until death or study closure (+/- 1 month) whichever comes first. Patients should be seen up to the 2 year point at the treating institution. If the patient is unable to be seen at the treating institution, copies of office visit notes including labs with local oncologist should be obtained until year 5 per schedule above. Initiation of all anticancer therapy for current remission and first anticancer therapy for relapse will be documented.

If a patient is removed from treatment for reason(s) other than progression or full consent withdrawal, follow for survival/relapse until death or study closure.

For patients who are registered with tissue submitted for the study and are FLT3 negative or other condition, no further information will be collected after baseline demographics, sample submission, sample results and final diagnosis. For eligible patients randomized to the trial, but do not receive any protocol therapy, baseline, safety [as applicable] and end of treatment follow-up information per Section 10 will also be collected.

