## 12 Statistical Considerations

### 12.1 Study Design & Sample Size Considerations

This is a randomized, open-label Phase II study comparing gilteritinib to midostaurin in patients receiving standard induction therapy with cytarabine and daunorubicin in FLT3 mutated AML. Patients will be stratified according to FLT3-TKD vs. FLT3-ITD mutation. Patients with FLT3-ITD mutation will undergo further stratification with NPM1 mutation status (positive vs. negative) and signal ratio (high [ $\geq 0.5$ ] vs. low [ $<0.5$ ] of FLT3 Wild Type). Patients will be randomized to receive standard induction treatment (cytarabine and daunorubicin) with either gilteritinib or midostaurin. If achieving CR or CRi, these patients will go on to receive standard consolidation treatment of high-dose cytarabine with the study drug received during induction (gilteritinib or midostaurin). Patients may proceed to allogeneic transplant after induction or after 0-4 cycles of chemotherapy consolidation. The primary objective of this study is to assess the FLT3 mutation negative CRc (includes CR and CRi) rate of patients who receive gilteritinib compared to those who receive midostaurin in addition to standard therapy with cytarabine and daunorubicin after induction. FLT3 mutation negativity is evaluated by PCR at the end of induction.

Based on a retrospective study performed at John-Hopkins, we assume with the control arm of cytarabine, daunorubicin and midostaurin, the FLT3 mutation negative CRc rate after induction is 40%. With 170 eligible patients with allocation ratio of 1:1 to the two arms, the study will have 80% power to detect an improvement of 20% in the FLT3 mutation negative CRc rate in the gilteritinib arm (i.e., from 40% to 60%) at the one-sided significance level of 0.05 based on Fisher's exact test. Accounting for 5% ineligibility, we will need a total of 179 patients.

Assume 7 FLT3 mutated patients will be accrued each month, the accrual of the study will be completed in 2.1 years.

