The CRc (CR or CRi, as defined in Section 9) rate of patients with FLT3 mutated AML who receive gilteritinib will also be compared to those who receive midostaurin. The CRc rate will be compared using Fisher's exact test. Two-sided 90% confidence interval on the difference in the CRc rate will be provided based on the normal approximation to the difference of two independent binomial proportions with continuity correction. One of the secondary objectives of this study is to compare event free survival (EFS) of patients who receive gilteritinib to those who receive midostaurin in addition to cytarabine and daunorubicin after induction and high-dose cytarabine after consolidation. EFS is defined as time from study randomization to the date of induction treatment failure, relapse after CRc or to death from any cause after CRc, whichever comes first. For patients alive without induction treatment failure or relapse after CRc, EFS will be censored at the date of the last disease evaluation. The main analysis of EFS is to set the event date for induction treatment failure on day 1 of randomization.

We assume with the control arm of cytarabine/daunorubicin plus midostaurin, for FLT3 mutated patients, the cure rate of EFS is 25% and the median EFS for the non-cure patients is 6 months. With approximately 170 eligible patients, the study will have 80% power to detect 38% reduction in hazard rate in EFS in the gilteritinib arm, using one-sided log rank test at the significance level of 0.05 and assuming 2 years of follow-up. The number of EFS events needed is about 110.

We will also assess OS of patients who receive gilteritinib to those who receive midostaurin in addition to cytarabine and daunorubicin after induction and high-dose cytarabine after consolidation. OS is defined as the time between randomization and death from any cause. The censored follow-up time for patients without death information is the date of last contact.

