The final analysis of EFS and OS will be performed when the full information of EFS is reached (i.e., 110 events have occurred). Estimates of EFS and OS, including medians and confidence intervals, will be calculated using the Kaplan-Meier method. Comparison of EFS and OS between treatment arms will be conducted using the one-sided stratified log-rank test with FLT3 mutation (TKD vs ITD), FLT3-ITD mutation signal ratio (high  $\geq 0.5$  vs. low  $<0.5$  of FLT3 Wild Type), and NPM1 mutation status, the same stratification factors used in randomization. Cox proportional hazards models, stratified on the same factors above, will also be used to assess the treatment effect.

A sensitivity analysis of EFS will be performed where follow-up will be censored at the start of transplantation.

Comparison of CRc rate, EFS and OS between treatment arms will also be conducted in patients with de novo AML, t-AML and AML-MRC separately; and in patients with favorable, intermediate, and adverse risk separately, determined by 2017 ELN risk classification.

To determine the predictive value of Minimal Residual Disease (MRD) positivity and negativity post induction therapy. EFS and OS of the patients who achieved MRD negative after induction will be compared with those who did not. All CRc patients who have MRD response evaluated post induction will be included into this analysis. The interaction of treatment and MRD status will be tested in the Cox regression model. If a strong interaction effect is detected, the treatment effect will be looked at within MRD+ and MRD- patients separately.

The correlation between MRD by molecular studies and morphology will be assessed. McNemar's test will be used to assess the concordance of the measurements.

For patients who are FLT3 mutation positive after induction and administered consolidation, the FLT3 mutation negative CRc rate after first cycle of consolidation and their corresponding 90% confidence intervals will be given by treatment arm.

To assess the correlation of FLT3 mutation with outcome, the EFS and OS of those patients with FLT3-TKD mutation will be compared with patients with FLT3-ITD mutation. Among those patients with FLT3-ITD mutation, EFS and OS will be compared among those with ITD signal ratio >0.5 with those ≤ 0.5 of FLT3 Wild Type.

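### The final EFS and OS analysis waits for 110 EFS events with no calendar limit, and under the plan's own assumptions about 29% of trials would never reach that count

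*Protocol*

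**What the plan says.** Protocol 12.2.2 sets the timing: "The final analysis of EFS and OS will be performed when the full information of EFS is reached (i.e., 110 events have occurred"). SAP 7.6.7 repeats the sentence, and SAP section 8 plans no changes from the protocol.

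The count comes from the EFS power statement in protocol 12.2.2. For the control arm, "the cure rate of EFS is 25% and the median EFS for the non-cure patients is 6 months". The claim, based on about 170 evaluable patients, is that "the study will have 80% power to detect 38% reduction in hazard rate in EFS in the gilteritinib arm". The test is a log-rank test, one-sided at 0.05, and the calculation takes follow-up to be two years. The required count is then given: "The number of EFS events needed is about 110".

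The two years appear only in that power assumption, not in the rule for when to analyse. Follow-up under protocol 7.2 continues, "then annually for progression and survival until death or study closure (+/- 1 month) whichever comes first", and no date is attached to closure. The EFS interim in protocol 12.3.1 is also tied to events (50% of information) and can stop the study only for inefficacy. The primary analysis of FLT3-negative composite complete response (CRc) has its own trigger: completion of induction and availability of MRD data.

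**The concern.** An event-only trigger is safe when the target sits well below the number of events the trial can produce. Here EFS is modelled with a cured fraction, so the curves flatten and the supply of events is finite. If the effect applies to the whole EFS curve, the gilteritinib arm levels off at 0.25^0.62 = 42% event-free, and 170 patients yield about 113 events however long one waits. A target of 110 leaves almost no margin.

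If gilteritinib works as planned, the final EFS and OS results could come well after two years, or the condition might not be met before the study closes. Someone would then have to choose a cut-off after EFS curves and a hazard ratio by arm exist from the interim. The rule is also least likely to be met when the drug works best.

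**Working it through.** **Inputs.** From protocol 12.2.2: control-arm cure 25%, median 6 months in the non-cured, hazard ratio (HR) 0.62, one-sided alpha 0.05, 80% power, about 170 patients. From protocol 12.1: 1:1 allocation (85 per arm) and the accrual rate: "Assume 7 FLT3 mutated patients will be accrued each month, the accrual of the study will be completed in 2.1 years". My assumptions: uniform accrual over 179/7 = 25.6 months; follow-up counted from last entry; no losses; no late deaths in remission.

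**1. The plan's 110.** Schoenfeld: d = 4(1.645 + 0.842)² / (ln 0.62)² = 108.2. Power is 80.6% at 110 events, 79.3% at 106 and 77.2% at 100. The stated figure is reproduced.

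**2. Expected events.** Control: S0(t) = 0.25 + 0.75 exp(−ln2 · t/6). Gilteritinib: S1(t) = S0(t)^0.62. Averaging 1 − S over the entry times, 24 months after last entry, gives event probabilities of 0.735 and 0.561. Expected events = 85 × (0.735 + 0.561) = 110.2, with a standard deviation of about 6.1. If instead every patient had exactly 24 months, 104.7 events would be expected, so counting from last entry is the reading that returns the plan's 110.

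**3. Chance of at least 110 events** (exact sum of two binomials, 85 per arm):

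| Months after last entry | Expected events | Chance of 110 |
|---|---|---|
| 24 | 110.2 | 54.6% |
| 36 | 112.1 | 66.9% |
| 60 | 112.7 | 70.5% |
| Unlimited | 112.8 | 70.7% |

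So about 29% of trials never reach 110 in this model. With accrual of 170/7 = 24.3 months, the 24-month figure is 53.9%.

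**4. Sensitivity.**

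| Change from base case | 24 months | 60 months |
|---|---|---|
| HR 0.55 | 32% | 47% |
| HR 0.70 | 77% | 88% |
| HR 0.80 | 92% | 97% |
| 165 patients | 33% | 49% |
| 174 patients | 70% | 83% |
| 179 patients | 85% | 93% |
| Late deaths 1% a year (assumed) | 66% | 87% |
| Late deaths 3% a year (assumed) | 84% | 99% |
| Losses 2% a year (assumed) | about 44% | 60% |
| Losses 5% a year (assumed) | 31% | 44% |
| Losses 2% and late deaths 1% (assumed) | 56% | 78% |

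The documents give no rate for losses or late deaths. Late deaths are modelled as multiplying both curves by exp(−bt), and losses as exponential.

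**5. Alternative reading of the effect.** If 25% are cured in both arms and the HR acts only on the non-cured, 97% of trials have 110 events by 24 months. Simulated power is then about 45%, so this reading does not match the stated 80%.

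**6. What a date limit does to power.** Log-rank simulation of the base case, 20,000 trials, standard error 0.3 points:

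| Rule | Power | Limit applies in |
|---|---|---|
| Events only | 80.2% | – |
| 110 or 24 months | 79.8% | 46% |
| 110 or 36 months | 80.1% | 33% |

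The events-only figure analyses trials that never reach 110 at the plateau, which the written rule does not provide for. When the 24-month limit applies, the median count is 106 (5th percentile 98).

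**The case against.** The strongest reply is that no inferential harm is shown. Power is the same with or without a limit, no type I error problem arises, and the endpoints are secondary in a Phase II trial. Event-driven analyses without a date are common, and a target equal to its expected count will be missed about half the time at that date by arithmetic alone. All of this is right. What stands against it is the ceiling: with a plateau, waiting does not guarantee the count.

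The percentages also depend on the base case. SAP 7.4.2 describes eligible patients broadly, so more than 170 may be analysed. Late deaths would add events, because EFS runs to "relapse after CRc or to death from any cause after CRc, whichever comes first", patients may be up to 70 and transplant is allowed. Dating induction failures at day 1 of randomisation is not modelled and would shift the 24-month figure. These points stand. The 55% should be read as one value in a range from about 31% to 97%; the missing date does not depend on it.

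On bias, protocol 12.3.2 restricts interim outcome data to the study statistician and the DSMB, a cut-off could be set from the pooled event count, and SAP 2.1 requires deviations to be agreed and documented. These safeguards reduce the risk of a cut-off informed by results. They do not pre-specify one.

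**Conclusion.** The point holds as an inexpensive improvement. Neither document gives a calendar alternative to 110 EFS events. If HR 0.62 acts on the whole curve, with 170 patients, no losses and no late deaths, the condition is met in about 55% of trials at the two years assumed for power (counted from last entry), in 67% at three years and in at most 71%. The missing date is certain from the text. The percentages move with the number analysed, the true effect, late deaths and losses, none of which the plan fixes tightly enough to guarantee 110. The event target itself is correct, and the primary analysis is untouched.

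**What to change.** In protocol 12.2.2 and SAP 7.6.7, state that the final EFS and OS analysis takes place at 110 EFS events or [24] months after the last patient is randomised, whichever comes first. Twenty-four months matches the power assumption; 36 months also closes the gap and displaces the event target less often. The choice is the sponsor's and should be fixed before any EFS result by arm is seen. If the EFS interim has already been run, people without access to it should set the date. Longer-term OS can follow as an update, since follow-up continues.

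**Cost.** One sentence in each document. A protocol amendment needs sponsor and IRB approval under protocol 14.1. Because SAP 2.1 says the SAP supersedes the protocol's statistical section, an SAP change with an entry in SAP section 8 may be enough. In the base case, a 24-month limit replaces the event target in about 46% of trials and a 36-month limit in about 33%, with power near 79% at the typical 106 events. OS follow-up is shorter than if one waited: when the limit applies, mean potential follow-up is 24 + 25.6/2 ≈ 37 months, or 36 + 25.6/2 ≈ 49 months.

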### 1.2 Background/Rationale

An overall CR rate of 50% to 80% can be expected with standard induction chemotherapy. Consolidation therapy is given with the goal of decreasing the risk of relapse and improving survival. However, presence of a FLT3 mutation in AML patients of any age is a poor prognostic factor. In these patients, although the CR rate with standard chemotherapy regimens is generally equivalent, the relapse rate, disease free survival (DFS), event free survival (EFS), and overall survival (OS) at 5 years are significantly worse. The addition of a targeted agent against FLT3 offers the possibility for significant therapeutic advantage in AML patients expressing FLT3, through both an additive effect on leukemia cell kill, as well as through potentiation of chemotherapy-induced cell death.

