### 12.3 Planned Interim Futility Analyses

#### 12.3.1 Interim Analysis of FLT3 Mutation Negative CRc Rate and EFS

An interim futility analysis of FLT3 mutation negative CRc rate will be performed when 90 (i.e., 50% of 179) patients have MRD response data available. The PrECOG Data Safety Monitoring Board (DSMB) may consider stopping the study for inefficacy if the observed FLT3 mutation negative CRc rate in the gilteritinib arm is lower than the control arm. The FLT3 mutation negative CRc rate (and CR rate) with two treatment arms combined will also be calculated. Upon the approval of the DSMB, it may be released to the study team to guide the design in other AML Phase III trials.

When the last patient has completed the induction treatment and all patients have MRD response data available, the final analysis of FLT3 mutation negative CRc rate will be performed. At that time, if the information fraction of EFS >50% (i.e., more than 55 EFS events have occurred), an interim futility analysis of EFS will be performed as well. Otherwise, the interim analysis of EFS will be performed later until 50% of information is reached. In the interim analysis of EFS time, the Kaplan-Meier curve for each arm and the point estimate and two-sided 90% confidence interval of hazard ratio (gilteritinib arm vs. control arm) will be provided. If the lower bound of the 90% confidence interval of HR is above 1, the study may be permanently terminated for inefficacy in EFS.

The interim futility analysis of FLT3 mutation negative CRc rate is complete and stopping criteria was not met. The study will continue as planned.

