## **7. GENERAL STATISTICAL CONSIDERATIONS**

This section will go into detail about the statistical approaches and methodology for this study analysis. Statistical analysis and programming of tables and listings will be conducted by QDS, using SAS® Release 9.4 (SAS Institute Inc., Cary, North Carolina, USA).

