### 7.6.7. Overall Survival (OS)

OS is defined as the time between randomization and death from any cause. The censored follow-up time for patients without death information is the date of last contact.

The final analysis of EFS and OS will be performed when the full information of EFS is reached (i.e., 110 events have occurred). Estimates of EFS and OS, including medians and confidence intervals, will be calculated using the Kaplan-Meier method. Comparison of EFS and OS between treatment arms will be conducted using the one-sided stratified log-rank test with FLT3 mutation (TKD vs ITD), FLT3-ITD mutation signal ratio (high  $\geq 0.5$  vs. low  $<0.5$  of FLT3 Wild Type), and NPM1 mutation status, the same stratification factors used in randomization. A multivariate Cox proportional hazards model, stratified on the same factors above, will also be used to assess the treatment effect.

Comparison of EFS and OS between treatment arms will also be conducted in patients with de novo AML, t-AML and AML-MRC separately; and in patients with favorable, intermediate, and adverse risk separately, determined by 2017 ELN risk classification.

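### EFS induction failures are tied on Day 1 by design, yet no tie method is named for the Cox model; under Breslow the hazard ratio drifts slightly toward 1 and its interval over-covers

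*Protocol*

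**What the plan says.** Protocol 12.2.2 fixes the date of one kind of EFS event by rule: "The main analysis of EFS is to set the event date for induction treatment failure on day 1 of randomization". SAP 5.6 and 7.6.6 carry the same rule.

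The main EFS comparison is a one-sided stratified log-rank test. The Cox model comes second. The protocol says "Cox proportional hazards models, stratified on the same factors above, will also be used to assess the treatment effect"; SAP 7.6.7 says "A multivariate Cox proportional hazards model, stratified on the same factors above, will also be used to assess the treatment effect". Neither document says how ties are handled. On software, SAP 7 states only that programming is done "using SAS® Release 9.4".

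A hazard ratio also enters a decision. At the EFS interim (Protocol 12.3.1, SAP 7.7), "the point estimate and two-sided 90% confidence interval of hazard ratio (gilteritinib arm vs. control arm) will be provided", and the study may be stopped for inefficacy if the lower limit lies above 1.

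Neither document gives a design value for CRc or for induction failure. The nearest figures are background ones. Protocol 1.2 says "An overall CR rate of 50% to 80% can be expected with standard induction chemotherapy". Protocol 1.3.4 reports a phase 1 CRc of 90.3% (28/31) in FLT3-mutated patients given gilteritinib at 80 mg/day or more.

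**The concern.** Most survival analyses have a few incidental ties, and the tie method hardly matters. Here the plan itself puts a whole class of events at one time point.

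Breslow keeps every failing patient in the risk set for all events at that time. On Day 1 it therefore estimates a ratio of failure risks instead of a hazard ratio, and a risk ratio lies nearer to 1. Its standard error also ignores the shrinking of the risk set, so it exceeds the real spread of the Breslow estimate.

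At stake are the reported EFS hazard ratio, the calibration of its interval and, if the interim interval comes from the same model, how readily the inefficacy criterion flags harm. Leaving the method open also leaves a choice that could be made after data are seen in an open-label trial.

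**Working it through.** **1. The plan's own EFS figure.** Protocol 12.2.2 states that "the study will have 80% power to detect 38% reduction in hazard rate in EFS in the gilteritinib arm". The error rate there is 5%, one-sided, and the event count is about 110. By Schoenfeld, events = 4(1.645 + 0.842)²/(ln 0.62)² = 4 × 6.183/0.2285 ≈ 108.2, rounded up to 109. With 110 events the power is 80.6%. The stated figure is reproduced.

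**2. How many events are tied.** Inputs: 170 eligible patients (Protocol 12.1) and 110 events. Tied share = 170 × (1 − CRc)/110.

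| CRc, both arms | Day-1 failures | Share of 110 events |
|---|---|---|
| 90% | 17 | 15% |
| 80% | 34 | 31% |
| 70% | 51 | 46% |
| 60% | 68 | 62% |
| 50% | 85 | 77% |

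**3. Day 1 alone.** If a hazard ratio of 0.62 holds from the start and a proportion p of controls fails, then 1 − (1 − p)^0.62 fail on gilteritinib. The risk ratio is [1 − (1 − p)^0.62]/p. For p = 20%, 30% and 40% this is 0.646, 0.661 and 0.679. The later, mostly untied events dilute the shift.

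**4. The whole EFS curve at the final analysis.** Simulation with 170 patients 1:1, 24.3 months of accrual, 25% control cure, a 6-month median in the non-cured and HR 0.62 throughout. The cutoff is 110 events or 24 months after accrual. Five equal strata and uniform accrual are assumptions. There were 6,000 runs per column.

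| Control induction failure | 19.5% | 29% | 38.5% |
|---|---|---|---|
| Tied share of events | 25% | 38% | 51% |
| HR, Breslow | 0.625 | 0.632 | 0.645 |
| HR, Efron | 0.618 | 0.618 | 0.620 |
| Mean SE of log HR, both methods | 0.200 | 0.200 | 0.199 |
| True SD of the Breslow estimate | 0.195 | 0.190 | 0.182 |
| Coverage of a 90% interval, Breslow | 91.2% | 91.6% | 92.1% |
| Coverage of a 90% interval, Efron | 90.4% | 90.4% | 90.3% |
| One-sided Wald power, Breslow | 77% | 76% | 73% |
| One-sided Wald power, Efron | 78% | 78% | 78% |

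Log-rank power is 78% to 79% in all three columns. Breslow's SE exceeds the true spread of its estimate by 2%, 5% and 9%. An unstratified variant at 40% failure gave 92.4% coverage. Other runs of the same design at 20/30/40% failure gave Breslow HRs of 0.630/0.638/0.652 and 0.631/0.644/0.650, against Efron values of 0.623 to 0.629.

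At HR 1, Breslow coverage was 90.5/92.6/93.8% in the tabulated set-up and 92.0/92.6/94.6% in a second set at 20/30/40% failure.

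**5. Few failures.** At 15% control failure (400 runs, about 21 tied events) Breslow gave 0.620 and Efron 0.618, with coverage of 90.8% and 90.5%. At 10% failure (700 runs) the HRs were 0.612 and 0.611.

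**6. The interim criterion.** The analysis was placed 60 days after accrual ends (assumption), with 4,000 runs per setting. At a true HR of 1.6 the lower 90% limit exceeded 1 in 76/74/70% of trials with Breslow and 79/79/80% with Efron, for control failure of 19.5/29/38.5%. Unrounded, the gaps are 2.6, 5.3 and 10.3 points. Two other sets of runs at 20/30/40% failure gave gaps of 3/5/11 and 2/7/12 points. At HR 1 the criterion was met in 4.5/4.0/2.5% with Breslow and 5.0/5.3/4.4% with Efron. Under HR 1.6 the simulated trials already had 116 to 124 events at this look, so these figures describe a late interim, not one at 55 events.

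**The case against.** **The effect may be absent.** The CR range in Protocol 1.2 concerns standard chemotherapy in general. It is not CRc with a FLT3 inhibitor after up to two inductions. The phase 1 CRc of 90.3% is closer to this trial, and at that level the difference is negligible. This stands as a statement about size. The documents give no design value, so the range has to be shown.

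**The software chain is assumed.** SAS 9.4 is named, but no procedure option is. Output templates sit in a separate document. Protocol 12.3.2 restricts interim outcome analyses to the study statistician and the DSMB, with no software named, and the interim text does not say that the hazard ratio comes from a Cox model. All of this stands, so the conclusion is conditional.

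**Efron is not automatically the truth.** Induction failure is a binary outcome placed on Day 1 by convention, and a risk ratio is a natural measure for it. This stands in part. If the drug acts differently on induction failure and on later relapse, no single hazard ratio is correct. However, the plan sizes EFS on one hazard reduction, and the shift is measured against that.

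**Little depends on it.** EFS is secondary and its main test is the log-rank test. The shift in log HR is about 0.01 to 0.04 against an SE of 0.20. The interim stop is discretionary, and Breslow makes it less likely, so false-positive risk does not rise. This stands, and it makes the point minor.

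A reader might also infer more than the documents support:
- That a definite share of events, such as a quarter to a half, is tied. No such share is stated; that range would need a CRc of about 84% to 68%.
- That Breslow widens the interval. On the log scale its SE equals Efron's; the fault is over-coverage.
- That the final Cox hazard ratio carries a stated 90% interval. That level is given for the hazard ratio only at the interim.
- That the interim criterion loses a nominal error rate. The plan states none.

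**Conclusion.** The gap is real and small. The plan ties all induction failures on Day 1 and leaves the tie method open. If Breslow is used, a true EFS hazard ratio of 0.62 reads about 0.625 to 0.65 at 20% to 40% control induction failure, with almost no change at 10% to 15%. A nominal 90% interval covers about 91% to 93% at HR 0.62 and mostly 92% to 95% at HR 1. If the interim interval comes from this model, the criterion is met roughly 3 to 10 points less often when gilteritinib is truly harmful (HR 1.6).

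This rests on three assumptions: the Breslow default is left in place, one hazard ratio also holds on Day 1, and induction failure lies in the simulated range. The stratified log-rank comparison and the primary endpoint are untouched. It is an optional improvement, not a defect that threatens the trial's conclusions.

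**What to change.** In SAP 7.6.6, 7.6.7 and 7.7, state that all EFS Cox models use Efron ties (TIES=EFRON) or the SAS exact method (TIES=EXACT), and that this applies to the hazard ratio, its confidence interval and the interim criterion. Say in 7.7 that the interim hazard ratio comes from this model. If the protocol is amended for other reasons, align 12.2.2 and 12.3.1.

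The cost is one phrase in the SAP, one option in the program and slightly more computing time. Sample size, event count and the log-rank test stay as they are.
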